7.1.1 Sorafenib Dose Modifications

Table 1. Sorafenib Dose Modifications

Toxicity		Sorafenib Modification
Cardiac		
Grade \geq 2 acute coronary syndrome (myocardial ischemia) or Grade \geq 2 myocardial infarction		Discontinue sorafenib permanently.
Heart failure	Grade 3	
 Interrupt until \leq grade 1; upon resumption, decrease by 1 dose level. If no recovery after 30 day interruption, discontinue sorafenib permanently unless patient is deriving clinical benefit; confer with PI.
	Grade 4	Discontinue sorafenib permanently.
Skin and Subcutaneous Disorders		
Palmar-plantar erythrodysesthesia syndrome (PPE) (hand-foot syndrome)		See Table 2 'Sorafenib Dose Reduction Guidelines for PPE (Hand-Foot Syndrome).'
Grade 2 rash acneiform		At investigator's discretion, consider holding and/or reducing sorafenib to the next lower dose.
Grade 3 or grade 4 rash acneiform		Hold sorafenib. 
 Re-evaluate at least weekly until resolution to \leq grade 1 or tolerable grade 2. Re-start sorafenib at one dose reduction. If toxicity persists > 14 days, discontinue sorafenib. Patients with grade 4 acneiform rash related to sorafenib may be taken off sorafenib at investigator's discretion.
Stevens-Johnson syndrome or toxic epidermal necrolysis		Discontinue sorafenib if Stevens-Johnson Syndrome or toxic epidermal necrolysis are suspected.
Gastrointestinal Disorders		
Perforation (esophageal, gastric, colonic, duodenal, ileal, jejunal, rectal, or small intestine)		Discontinue sorafenib permanently.

Investigations	

Grade \geq 3 ALT increase in the absence of another cause or
 
AST or ALT $>$3x ULN with bilirubin $>$2xULN in the absence of another cause; or
 
Grade \geq 1 Alkaline phosphatase in the absence of known bone pathology with grade \geq grade 2 bilirubin increase; or
 
any 1 of the following INR \geq 1.5, ascites and/or encephalopathy in the absence of underlying cirrhosis or other organ failure related to drug-induced liver injury
	
Discontinue sorafenib permanently.

Lab abnormalities - not clinically significant
 
Note: For clinically significant lab abnormalities follow the dose modification guidelines for "All Other Non-Hematologic Toxicities."
	
Continue sorafenib and institute supportive measures. At investigator's discretion, consider holding and/or reducing sorafenib to the next lower dose.

Grade 3 electrocardiogram QT corrected interval prolonged	
See also Section 7.4.8
 
Hold sorafenib
 
 • Check and immediately administer potassium to achieve levels of ≥ 4 and magnesium to levels of ≥ 2. • Consider chronic oral supplementation of potassium and/or magnesium. • Review with principal investigator prior to patient's next scheduled treatment, considering the following options: 
 ○ STOP sorafenib until QTc recovers to pre-study treatment baseline (grade 1 or less, or ≤ 480ms). ○ When QTc returns to baseline, reinstitute sorafenib cautiously, with additional QTc monitoring at earliest possible follow-up opportunity, but no more than 8 days from reintroduction of sorafenib. ○ If QTc prolongation event felt attributable to sorafenib, reduce sorafenib to the next lower dose. • For recurrent QTc grade 3 felt attributable to sorafenib despite dose reduction, consider permanent discontinuation of sorafenib.
Grade 4 electrocardiogram QT corrected interval prolonged	Discontinue sorafenib. Do not restart.
Nervous System Disorders (potentially reflective of cardio-toxicity)	
Grade 2 pre-syncope or grade 3 syncope	
See also Section 7.4.8
 
 • Obtain ECG for cardiology review/consultation. • Check and immediately administer potassium to achieve level of ≥ 4 and magnesium to level ≥ 2. • If ECG shows new dysrhythmia or QTc \geq grade 2 (> 480ms), hospitalize for monitoring with Cardiology consultation. • STOP sorafenib until any potassium and magnesium abnormalities are corrected, symptoms resolved and QTc returns to grade 1 or less (≤ 480ms). • Reintroduce sorafenib cautiously, with input from Cardiology and with additional QTc evaluation, either concurrent with reintroduction or at earliest possible follow-up opportunity and no more than 8 days from reintroduction. • If event felt attributable to sorafenib, reduce sorafenib to the next lower dose. • Consider chronic oral supplementation of potassium and/or magnesium. • For recurrent syncope or near-syncope felt attributable to sorafenib, consider permanent discontinuation of sorafenib.
Vascular Disorders	
Hypertension	See Table 3 'Management of Hypertension.'
All Other Non-Hematologic Toxicities	
Grade ≥ 2 hemorrhage (requiring medical intervention)	Discontinue sorafenib permanently.

Any grade 2 non-hematologic toxicity that is persistent, intolerable, or unresponsive to optimal management	At the treating investigator's discretion, consider holding or continuing treatment at 1 dose reduction.
Grade 3	
1st occurrence:
 
 • Hold sorafenib until resolution to ≤ grade 2 or baseline. • When resuming sorafenib, decrease the sorafenib dose by one dose reduction. • If toxicity persists >14 days of treatment delay, discontinue sorafenib. 
No improvement within 7 days; or 2nd or 3rd occurrence:
 
 • Hold sorafenib until resolution to ≤ grade 2 or baseline. • When resuming sorafenib, decrease the sorafenib dose by 2 dose reductions. • If toxicity persists >14 days of treatment delay, discontinue sorafenib 
4th occurrence:
 
 • Hold sorafenib until resolution to ≤ grade 2 or baseline. • When resuming sorafenib, decrease the sorafenib dose by 3 dose reductions. • If toxicity persists >14 days of treatment delay, discontinue sorafenib
Grade 4	Discontinue sorafenib permanently.

7.1.2 Sorafenib Dose Modification Guidelines and Management for PPE (Hand-Foot Syndrome)

Table 2. Sorafenib Dose Reduction Guidelines for PPE

Grade	Occurrence	Action
Grade 1	1st occurrence or recurrence	Continue sorafenib and institute supportive measures for symptomatic relief.*
Grade 2: Moderate and painful skin changes of hands and/or feet such as peeling, blisters, bleeding, hyperkeratosis, erythema, swelling; and/or any such changes that are limiting instrumental activities of daily living (preparing meals, shopping for groceries, using the telephone, managing money, etc).	1 st occurrence	Decrease sorafenib dose by one dose level and institute or continue supportive measures for symptomatic relief.* If no improvement within 7 days, see below.
	No improvement within 7 days	Stop sorafenib treatment until toxicity resolves to grade 0-1. When resuming treatment, continue at ongoing dose reduction. Institute or continue supportive measures for symptomatic relief.*
	Recurrence beyond 1 st occurrence	Stop sorafenib treatment until toxicity resolves to grade 0-1. When resuming treatment, decrease sorafenib by 1 dose level. Institute or continue supportive measures for symptomatic relief.*
Grade 3: Severe and painful skin changes of the hands and/or feet, such as moist desquamation, ulceration, blistering, bleeding, hyperkeratosis, erythema, swelling; and/or any such severe changes or pain that are limiting self-care activities of daily living (bathing, dressing, feeding self, using toilet, taking medications or becoming bedridden).	1 st or 2 nd occurrence	Stop sorafenib treatment until toxicity resolves to grade 0-1. When resuming treatment, decrease sorafenib by one dose level. Institute or continue supportive measures for symptomatic relief.*
	3 rd occurrence	Discontinue sorafenib treatment.

*See also Section [7.4.7](#).

7.1.3 Sorafenib Dose Modification Guidelines and Management for Hypertension

The management of hypertension related to sorafenib, including the choice of antihypertensive medication, will be performed according to the treating physician's usual practice.

Every effort should be made to control BP by medical means other than sorafenib dose modification. If necessary, follow the sorafenib dose reduction instructions in [Table 3](#).

Table 3. Management of Hypertension Related to Sorafenib

Grade	Antihypertensive Therapy	Sorafenib Dosing
Grade 1 Prehypertension Systolic BP 120-139 mmHg or Diastolic BP 80-89 mmHg	None	
 • Continue sorafenib • Consider increasing BP monitoring
Grade 2 Asymptomatic and diastolic BP 90-99 mmHg	Treat with the aim to achieve diastolic BP < 90 mmHg 
 • If BP previously WNL, start antihypertensive • If patient is already on antihypertensive medication, increase the dose 	Continue sorafenib and increase BP monitoring
Grade 2 Symptomatic or persistent or Grade 2 Symptomatic increase in diastolic BP by > 20 mmHg (diastolic) or > 140/90 mmHg if previously within normal limits or Grade 3 Systolic BP ≥ 160 mmHg or Diastolic BP ≥ 100 mmHg or More than one antihypertensive medication or indication for more intensive therapy than previously used	Treat with the aim to achieve diastolic BP < 90 mmHg Start antihypertensive medication and/or Increase current antihypertensive medication and/or Add additional hypertensive medications	
 • Omit sorafenib until diastolic BP ≤ 90 mmHg, and if symptomatic, until symptoms resolve • When sorafenib is restarted, resume at 1 dose reduction step
Grade 4 Life-threatening consequences (eg, malignant hypertension, transient or permanent neurologic deficit, hypertensive crisis)	Per treating physician	Discontinue sorafenib permanently.

* If BP remains controlled for at least one cycle, dose escalation, **up to the enrolled dose level**, is permitted at the investigator's discretion.

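### Table 3 lets systolic pressure start a sorafenib hold but releases it on diastolic pressure alone, so asymptomatic Grade 3 systolic hypertension with diastolic at or below 90 requires no hold

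*Combined protocol and SAP*

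**What the plan says.** Section 7.1.3 leaves the management of sorafenib-related hypertension to the treating physician's usual practice. It adds: "Every effort should be made to control BP by medical means other than sorafenib dose modification". Table 3 is to be followed if necessary.

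One row of Table 3 covers symptomatic or persistent Grade 2 and all Grade 3 hypertension. Its parts are:

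- **Grade 3 pressure trigger:** "Systolic BP ≥ 160 mmHg or Diastolic BP ≥ 100 mmHg" (the row has other triggers, which do not matter here).
- **Treatment aim:** "Treat with the aim to achieve diastolic BP < 90 mmHg", by starting, increasing or adding antihypertensives.
- **Release of the hold:** "Omit sorafenib until diastolic BP ≤ 90 mmHg, and if symptomatic, until symptoms resolve".
- **Dose after release:** "When sorafenib is restarted, resume at 1 dose reduction step".

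A footnote allows later re-escalation if blood pressure stays controlled for at least one cycle. It does not define controlled.

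**The concern.** Systolic pressure can start the hold but has no part in ending it. For a patient whose problem is purely systolic, the release test looks at a measurement that was never abnormal, so the hold can end before the abnormality has been treated.

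Other sorafenib holds are released on the quantity that triggered them: Table 1 waits for QTc to return to 480 ms or less and for heart failure to reach Grade 1 or lower, and Table 2 waits for hand-foot syndrome to reach Grade 0 or 1. Nothing suggests that systolic pressure was meant to be ignored during treatment, since Table 3 uses it both to grade and to trigger.

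What is at stake is patient safety on restart. Table 3 itself lists hypertensive crisis and neurologic deficit as Grade 4 consequences. Grade 3 hypertension is exempt from the qualifying toxicities in Section 6.4.2, so neither the safety lead-in nor the sequential stopping rule counts it. Required visits under Section 7.5 become monthly after the first 8 weeks, so after a later restart the next required reading may be about four weeks away unless the physician checks sooner.

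**Working it through.** The plan gives no figure to reproduce. The check is to write the row as logic and apply it to readings.

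**Inputs (Section 7.1.3, Table 3).** S is systolic and D is diastolic pressure, in mmHg.

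- Grade 3 pressure trigger: S ≥ 160 or D ≥ 100.
- Release: D ≤ 90 and no symptoms.

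**Applied to asymptomatic illustrative readings:**

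| Reading | Trigger met | Release met at the same reading |
|---|---|---|
| 160/70 | yes | yes |
| 175/82 | yes | yes |
| 180/90 | yes | yes |
| 170/91 | yes | no |
| 170/95 | yes | no |
| 165/99 | yes | no |
| 150/100 | yes | no |
| 170/105 | yes | no |

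Over whole-number readings with S from 160 to 220 and D from 50 to 99, every asymptomatic case with D ≤ 90 meets release at onset, and none with D of 91 to 99 does. No case with D of 100 to 139 meets release at onset. No symptomatic case does either.

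**Diastolic fall required before release, asymptomatic patient:**

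- D ≥ 100: at least 100 − 90 = 10 mmHg.
- S ≥ 160 with D 91 to 99: 91 − 90 = 1 to 99 − 90 = 9 mmHg.
- S ≥ 160 with D ≤ 90: none. No systolic fall is required in any of the three cases.

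At 175/82, systolic is 175 − 160 = 15 mmHg above the trigger when release is met, so the minimum hold is 0 days.

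**Dose on restart (Section 7.1).** From full dose, one step goes from 400 mg twice daily (800 mg/day) to 400 mg daily.

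**Does another rule supply a systolic release value?**

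- Table 1 refers hypertension to Table 3. Its own Grade 3 release (Grade 2 or lower, or baseline) belongs to the rows for all other non-hematologic toxicities.
- Section 7 has a general sentence about omitting agents until Grade 1 or lower. It follows guidelines introduced for toxicities that Tables 1 to 4 do not cover, and Table 3 covers hypertension with its own release.
- Section 7.1 (Grade 1 or lower, after cycle 1) and the Table 3 footnote govern later escalation, not the restart.
- Exclusion 4.2.9 sets a systolic limit of 160 that persists under optimal treatment, but it applies at entry only.

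None of these clearly provides a systolic condition for the restart.

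**The case against.** The strongest reply is that Table 3 is a fallback. It applies if necessary, after other means, under the physician's usual practice. The release wording sets a minimum and does not order a restart. The row also calls for antihypertensive treatment and a lower sorafenib dose. All of this stands: zero days is the shortest permitted hold, not the expected course. But discretion is not a restart limit, and the row does set one for diastolic pressure.

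A second reply is that Section 7's general sentence (resolution to Grade 1 or lower) fills the gap, since it stands in a paragraph after the bullets for toxicities outside the tables. That reading is possible. It would, however, conflict with Table 3's specific release, under which diastolic 90 suffices although it lies above the table's Grade 1 diastolic range of 80 to 89. It would leave two rules rather than cure the omission.

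A third reply is that safety oversight remains: related Grade 4 hypertension still counts as a qualifying toxicity, and all adverse events are recorded (Section 8.4). That is correct and limits the seriousness of the point.

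A reader might also infer three stronger claims that the documents do not support:

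- **Every systolic-only trigger gives a zero hold.** It does not; at 170/95 diastolic must still fall by 5 mmHg.
- **Persistent systolic pressure would force repeated dose steps down to the lowest level.** The text does not say that one continuing episode counts as several, and the preface points the other way.
- **A patient ineligible at entry is being restarted.** Exclusion 4.2.9 concerns pressure that persists under optimal management, which is not the same as a newly treated episode.

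**Conclusion.** The concern holds for a defined group: asymptomatic patients with systolic of at least 160 and diastolic of at most 90 mmHg. For them the written rule requires no hold and permits a restart one dose step lower with systolic still in the Grade 3 range. This rests on reading Table 3's specific release as prevailing over Section 7's general sentence; on the other reading, the two rules conflict and still need to be reconciled.

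This is a minor safety correction that is worth making. It has no effect on type I error, power or sample size. The documents give no frequency for isolated systolic Grade 3 hypertension, so the number of patients affected cannot be estimated.

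**What to change.** In the Table 3 row that omits sorafenib, change the release to: diastolic at or below 90 mmHg and systolic below 160 mmHg, with symptom resolution as now. Add a systolic value to that row's treatment aim, for example below 140, which matches the table's Grade 1 ceiling of 139. The sponsor should set the final thresholds. With the amended release, 175/82 is held until systolic has fallen by more than 15 mmHg. A reading such as 159/88 would satisfy release while still above the Grade 1 range, which is why the aim needs a systolic value too.

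The cost is an amendment to two cells of one table. No extra test is needed, because the reading that gives diastolic also gives systolic. Holds for isolated systolic hypertension become slightly longer.

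Lead-in evaluability is little affected. Section 10.1 asks for twice-daily sorafenib on at least 21 of the first 28 days. For a patient at full dose, the existing step to 400 mg daily (read as once daily) already ends twice-daily dosing, and Section 7.1 allows escalation only after cycle 1. A patient who triggers before completing 21 such days fails that requirement whatever the length of the hold; one who triggers later has already met it.

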7.2 Sildenafil

Sildenafil dose reductions (to be followed decrementally in this order):

- 50 mg twice daily
- 25 mg twice daily
- 25 mg once daily
- If cannot tolerate lowest sildenafil dose, discontinue sildenafil

Sildenafil may be omitted for short periods at the treating physician's discretion, if it is believed that sildenafil is contributing to excess toxicity. If toxicities resolve to \leq grade 1, the sildenafil dose may be escalated at the treating physician's discretion but not beyond a patient's enrollment dose.

The following toxicities require immediate discontinuation of sildenafil therapy:

- Prolonged erection for more than 4 hours
- Sudden loss of vision in one or both eyes
- Sudden decrease or loss of hearing

7.3 Valproic Acid

If toxicity is observed that is thought to be due to valproic acid then serum valproate levels should be obtained. If supratherapeutic valproate levels are observed (as described in Section [1.7](#)) temporary interruption of valproate may be indicated until toxicity resolves to grade 1 or less. Upon resolution of toxicity, a repeat serum valproate level should be obtained. Resumption of valproic acid at a reduced dose to achieve a lower serum valproate level should be considered. In the setting of hypoalbuminemia, the serum valproate level may be falsely elevated and a free valproate level may be required.

Table 4. Valproic Acid Dose Modifications

Toxicity	Valproic Acid Modification
General Disorders: Hypothermia	
Lethargy, confusion, coma, significant alterations in major organ systems (cardiovascular and respiratory) may signal hypothermia	Consider holding valproic acid while evaluating serum valproic acid levels. Blood ammonia level may be evaluated at investigator discretion.
Grade 2 or greater hypothermia	Consider discontinuing valproic acid. Discuss with principal investigator.
Investigations: Other – Hyperammonemia	
Symptomatic elevated ammonia level. Ammonia measured only as clinically indicated for clinical findings of unexplained lethargy, vomiting or changes in mental status.	Consider holding valproic acid while measuring serum valproic acid and ammonia levels. Consider evaluation for underlying urea cycle disorder and discontinuing valproic acid for elevated ammonia level. Discuss with principal investigator. If liver toxicity is suspected: 
 • Discontinue valproic acid • Consider supplementation with L-carnitine
Investigations: Hepatotoxicity	
Grade 3 or grade 4 AST or ALT increase	Consider holding valproic acid while under evaluation to rule out hepatic dysfunction. Consider liver ultrasound, hepatology consult, tests of hepatic function (such as bilirubin, INR, GGT, ammonia). Consider supplementation with L-carnitine. If no alternative explanation for transaminitis can be determined (such as viral hepatitis, progressive underlying malignancy), discontinue valproic acid.
Gastrointestinal Disorders	
Abdominal pain, nausea, vomiting and/or anorexia that are not attributable to other causes can signal pancreatitis and require prompt medical evaluation	Consider holding valproic acid while under evaluation and ruling out pancreatitis.
Pancreatitis	Discontinue valproic acid. Note: Elevations in lipase are very common in patients taking sorafenib. A diagnosis of pancreatitis should not be made solely based on abnormal laboratory values.

Valproic acid should be immediately discontinued in the presence of significant hepatic dysfunction, suspected or apparent.

Patients should be monitored for the emergence or worsening of depression, suicidal thoughts or behavior, and/or unusual changes in mood or behavior.

Significant bleeding or coagulopathy is an indication for reduction of the dosage or discontinuation of valproic acid.

7.4 General Concomitant Medication and Supportive Care Guidelines

(see also Section [9](#))

- 7.4.1 Fluids should be administered as indicated to prevent/treat dehydration. Maintain appropriate electrolyte balance including correction of hypokalemia and hypomagnesemia, and hypophosphatemia, if possible, prior to and during study treatment. In those patients who demonstrate electrolyte abnormalities, oral supplementation should be considered as a standard supportive measure to keep magnesium levels at \geq LLN for the laboratory, potassium levels at \geq LLN for the laboratory, and phosphorus levels at or above 2.4 mg/dL.
- 7.4.2 Clinically significant diarrhea should be managed aggressively to prevent electrolyte abnormalities and dehydration.
- 7.4.3 Concurrent administration of other anti-neoplastic agents with the study combination regimen is prohibited.
- 7.4.4 Concurrent administration of organic nitrates or alpha-blockers with the study combination regimen is prohibited.
- 7.4.5 Cautionary statements about other concurrent medications:

Addition of any STRONG CYP inhibitors and/or inducers per examples on the FDA website

(<http://www.fda.gov/Drugs/DevelopmentApprovalProcess/DevelopmentResources/DrugInteractionsLabeling/ucm093664.htm>) during study participation should prompt treating investigator awareness of possible interactions. Specifically:

- Caution should be observed if sorafenib is to be coadministered with CYP3A4 inducers such as rifampin, rifampicin, St. John's wort, phenytoin, carbamazepine, phenobarbital, and dexamethasone (for reference see <http://www.fda.gov/Drugs/DevelopmentApprovalProcess/DevelopmentResources/DrugInteractionsLabeling/ucm093664.htm>) may increase metabolism of sorafenib, decreasing sorafenib plasma concentrations
- Caution should be observed if sildenafil is to be coadministered with CYP3A4 or CYP2C9 inhibitors (for reference see <http://www.fda.gov/Drugs/DevelopmentApprovalProcess/DevelopmentResources/DrugInteractionsLabeling/ucm093664.htm>)

- 7.4.6 Caution should be observed if valproic acid is to be coadministered with any of the following: aspirin, carbapenem antibiotics (ertapenem, imipenem, meropenem), rifampin.

- 7.4.7 PPE (hand-foot syndrome)

Biopsy specimens of patients with PPE secondary to tyrosine kinase inhibition show hyperkeratosis, keratinocyte necrosis, and dermal inflammation. Recommended management strategies for skin toxicities consistent with PPE are summarized in the following sections:

7.4.7.1 PPE Prevention

- Before initiating treatment with sorafenib, check the condition of the patient's hands and feet. Suggest a manicure/pedicure, when indicated. Recommend use of a pumice stone for callus or rough spot removal. During sorafenib treatment, instruct patients to avoid pressure points and items that rub, pinch, or create friction.
- Instruct the patient to apply moisturizing lotions to their hands and feet twice a day throughout treatment.

